11.7 Steroid Use and Dose

Steroid use should be derived from the concomitant medications on the case report forms and recorded as “Yes”, “No”, or “not available”. A value of “No” should be assigned if, at the time-point, the subject is not on steroids or on physiologic replacement doses only (<2 mg dexamethasone or equivalent per day).

Average steroid dose no greater than 2 mg change from baseline should be abstracted to “stable”. If outside this range the steroid dose should be abstracted to “increased” or “decreased” accordingly. Steroid data should be within ± 5 days of the time-point response date, otherwise the data is considered “not available”.

11.8 Overall Objective Status

The overall objective status for an evaluation should be determined by combining the patient's radiographic response on target lesions, new disease, neurological status, and steroid dose/usage as defined in the table [below](#) for patients with *measurable* ($>10\text{mm} \times 10\text{mm}$) disease. Note that patients with possible PsP or pseudoresponse should be given the Objective Status of "Preliminary Progression" or "Preliminary Response", respectively. Once PsP, pseudoresponse, or true progression/response are confirmed, the Objective Status can be changed accordingly.

[figure not shown]
Guidelines for determining comprehensive objective status

Target lesions (current scan)	Target lesions (previous scan)	New sites of measurable disease ^a	Neurological status	Steroid usage	Steroid dose	Overall objective status
CR	Not Evaluated	No	Stable/Better	No	N/A	Preliminary CR
PR	Not Evaluated	No	Stable/Better	Any	Stable/Decreasing	Preliminary PR
PD	Not Evaluated	Yes or No	Stable/Better	Any	Stable/Increasing	Preliminary PD
PD	Preliminary or Confirmed PR/CR	No	Stable/Better	Any	Stable/Increasing	Preliminary PD
SD	Preliminary or Confirmed CR/PR or SD/NE	No	Stable/Better	Any	N/A	SD
PR	Preliminary PR	Yes or No	Stable/Better	Any	Stable/Decreasing	Confirmed PR
SD	Preliminary PR	Yes or No	Stable/Better	Any	Stable/Decreasing	SD (Preliminary PR → Confirmed PR)
SD	Preliminary CR	Yes or No	Stable/Better	Any	Stable/Decreasing	SD (Preliminary CR → Confirmed CR)
CR	Preliminary CR	No	Stable/Better	No	N/A	Confirmed CR
SD	Preliminary PD	No	Stable/Better	Any	Stable/Decreasing	SD (Confirmed PsP)
CR/PR/SD PD/NE	CR/PR/SD/PD/NE	Yes or No	Worse	Any	Stable/Increasing	Confirmed PD
PD	Preliminary PD	Yes or No	Any	Yes	Stable/Increasing	Confirmed PD

^aNote that new sites of measurable disease are added to the sum of bidimensional products or total lesion volume, or constitutes preliminary PD in the case of no measurable disease at baseline or best response

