11.2 Complete Response (CR)

Requires **all** of the following:

1. Disappearance of all enhancing measurable and non-measurable disease sustained for at least 4 weeks. The first scan exhibiting disappearance of all enhancing measurable and non-measurable disease is considered “preliminary CR”. If the second scan exhibits measurable enhancing disease with respect to the “preliminary CR” scan, then the response is not sustained, noted as pseudoresponse, PsR, and is now considered “preliminary PD” (note: confirmed PD requires at least two sequential increases in tumor volume). If the second scan continues to exhibit disappearance of enhancing disease or emergence of non-measurable disease (less than 10mm bidimensional product), it is considered a *durable CR* and the patient should continue on therapy until confirmed PD is observed.
2. Patients must be off corticosteroids (or on physiologic replacement doses only).
3. Stable or improved clinical assessments.

Note: Patients with non-measurable disease only at baseline cannot have CR; the best response possible is stable disease (SD).

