If the lesion(s) have increased $\geq 25\%$ sum of bidirectional product between MRI Scan N and N + 1, (indicating radiographic progression from MRI(N)), this is considered an “unsustained radiographic response” or “pseudoresponse”. These patients should be categorized as “preliminary radiographic progression”. If the investigator believes the patient can safely continue on therapy, then they should continue to treat and acquire a follow-up confirmatory scan [MRI(M)] at the next scan interval (8 weeks \pm 4 weeks from MRI Scan (N+1) or no less than 4 weeks minimum duration between preliminary PD and confirmed PD scans) to verify tumor growth and progression. If the patient has an increase $\geq 25\%$ sum of bidirectional product between MRI Scan N+1 and M, this is “Confirmed Progression”, *the patient should stop therapy* and the date of radiographic progression is the date of suspected progression, MRI(N+1). If the patient has SD/PR/CR on MRI(M) with respect to MRI(N+1), PsP is confirmed and the patient should continue on therapy. Patients will then continue on therapy and receive additional follow-up MRI scans [MRI(M)].

Alternatively, if the lesion has not increased from MRI(N), this is considered a “durable radiographic response,” the patient will continue on therapy, and the date of *preliminary* radiographic progression is the time point of an increase $\geq 25\%$ sum of bidirectional product (from Nadir) during the remainder of the study. The investigator can then decide whether to continue safely on therapy until progression has been confirmed and at the subsequent time point stop therapy if they feel the patient cannot safely continue therapy.

Stable Disease

If the lesion size has not increased or decreased beyond the set thresholds between Scan 1 and N, the patient is considered “stable.” Such patients will continue on therapy, and the date of *preliminary* progression is the time point of an increase $\geq 25\%$ sum of bidirectional product (from Nadir) during the remainder of the study. Upon preliminary progression the investigator can choose to either continue therapy and confirm progression or discontinue therapy. For cases with significant neurologic decline at the time of imaging progression as determined from MRI(N), a confirmatory scan at time point MRI(N + 1) may not be possible or necessary. For these cases, it is appropriate to define MRI(N) as the progression time point.

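### For measurable disease, the 11.8 status table confirms a CR despite a new measurable lesion, against 11.2, 11.5 and its own footnote, and it lacks rows for two routes to preliminary PD when neurology is stable or better

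*Combined protocol and SAP*

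**What the plan says.** Section 11.8 introduces its table with "The overall objective status for an evaluation should be determined by combining the patient's radiographic response on target lesions, new disease, neurological status" and steroid dose or usage, and limits it to measurable disease. The table is titled "Guidelines for determining comprehensive objective status".

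- **Preliminary PD rows.** Both require stable or better neurology and a stable or increasing steroid dose. In one, the previous scan is Not Evaluated and new sites may be Yes or No. In the other, the previous scan is "Preliminary or Confirmed PR/CR" and new sites must be No.
- **SD after Preliminary CR.** New measurable sites may be Yes or No. The outcome cell begins "SD (Preliminary CR → Confirmed CR".
- **Footnote a**, attached to the new-sites column, says that a new measurable site "constitutes preliminary PD in the case of no measurable disease at baseline or best response".
- **Section 11.2**, on measurable disease in the scan after a preliminary CR: "then the response is not sustained, noted as pseudoresponse, PsR, and is now considered" preliminary PD. The same item lets non-measurable disease reappear without losing the CR.
- **Section 11.5** compares the first growth of 25% or more with the smallest earlier measurement and calls it preliminary PD (item 1). It treats new measurable disease after a best response without measurable disease in the same way (item 2).
- **Section 11.9**, Stable Disease: "If the lesion size has not increased or decreased beyond the set thresholds between Scan 1 and N, the patient is considered" stable. The paragraph then dates preliminary progression at the first rise of 25% or more from nadir.

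Section 15.3.1 defines PFS from first vaccination to first documented progression, recurrence or death.

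**The concern.** The status at each scan feeds PFS, a secondary endpoint compared by log rank, and the response categories. Section 11.9 dates a confirmed progression back to the scan at which it was first suspected, so the scan that receives the preliminary label matters.

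The SD-after-Preliminary-CR row gives an answer opposite to the text, and it turns a progression into a confirmed response. The missing rows leave an ordinary sequence (stable scan, then growth, patient clinically stable) without a table entry. No sentence says how 11.2, 11.5, 11.8 and 11.9 rank for endpoint derivation. Two people working from the same measurements, one from the table and one from the text, could therefore record different statuses and, in the CR case, different PFS dates.

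**Working it through.** The plan states no figure to reproduce here. The check is of the table's logic against the text.

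**1. Row coverage.** I coded the table's 12 rows and enumerated new site (2) × steroid use (2) × steroid dose (3) = 12 combinations for each pairing of current and previous status, separately by neurology. Eight of the 12 have a stable or increasing dose, the condition that both Preliminary PD rows impose.

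| Current, previous, neurology | Combinations with a row (dose stable or increasing) | Result |
|---|---|---|
| PD, Not Evaluated, stable/better | 8 of 8 | Preliminary PD |
| PD, SD, stable/better | 0 of 8 (0 of all 12) | none |
| PD, SD, worse | 8 of 8 | Confirmed PD |
| PD, any preliminary or confirmed PR/CR, stable/better | 4 of 8 (new site No only) | Preliminary PD |
| PD, Preliminary PD, stable/better | 4 of 8 (steroid usage Yes only) | Confirmed PD |

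For SD after Preliminary CR with a new site and stable or better neurology there are 2 × 3 = 6 steroid combinations. Four return a confirmed CR, two have no row, and none returns preliminary PD.

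**2. The CR row followed through.** Take a preliminary CR at scan N. At N+1 the target lesions read SD, one new measurable lesion is present, and neurology and steroids are stable. At N+2 there is further growth of 25% or more.

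- By 11.2 and 11.9: pseudoresponse and preliminary PD at N+1, confirmed at N+2, dated N+1.
- By the table row: CR confirmed at N+1. The first possible progression label is at N+2, so the date moves by at least one interval, which 11.9 gives as 8 ± 4 weeks, that is 4 to 12 weeks.

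With new sites No, the row agrees with 11.2, because only non-measurable disease can then have reappeared. The Yes is what creates the conflict.

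**3. Growth after a stable scan (constructed example).** Post-RT baseline 4.0 cm²; scan 1, 4.1; scan 2, 5.4; scan 3, 7.0; neurology and steroids stable.

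- Scan 1: 4.1/4.0 = 1.025, SD.
- Scan 2: 5.4/4.0 = 1.35, preliminary PD by 11.5 item 1.
- Scan 3: 7.0/5.4 = 1.30, confirmed PD, dated scan 2 by 11.9.

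The table has no row at scan 2. At scan 3 its Confirmed PD row needs a previous Preliminary PD, which the table alone never assigned, and it also needs steroid usage Yes.

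**4. Can the share without a row be sized?** An illustrative model is (1 − f)(1 − r)(1 − w). Here f is the share of progressions seen at the first two-monthly scan, r the share preceded by PR or CR, and w the share with worse neurology. With exponential times, f = 1 − 2^(−2/m), which is 0.177 at m = 7.1 months and 0.125 at m = 10.4 months (medians in 6.2.2). The documents give neither r nor w. Taking r from 0 to 30% and w from 10% to 60% as assumptions:

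- highest: 0.875 × 1.0 × 0.9 = 0.79
- lowest: 0.823 × 0.7 × 0.4 = 0.23

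The range spans one half. In addition, 6.2.2 gives the 10.4 months for patients without radiographically evident disease and the 7.1 months for a gross-total-resection cohort. Neither is the measurable-disease population that the table covers.

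**The case against.** The strongest reply is that the protocol already answers both cases. Section 11.5 item 1 and the Stable Disease paragraph of 11.9 classify and date growth after a stable scan from measurements. The text just above the table also assigns a preliminary-progression status to possible pseudoprogression, with no condition on the previous scan. The table is called guidelines and holds no dates. This stands: the omission of PD after SD is a gap in the table, and it shifts a PFS date only if someone derives status from the table alone.

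For the CR row, one can say that the cell is nearly empty, since 11.4 bars SD when a scan qualifies as PD and footnote a sits on the same column. But the table scores target lesions and new sites in separate columns, and the row expressly admits a new measurable site and still confirms the CR. That is a contradiction, not only missing detail.

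Not Evaluated might mean that the previous status is disregarded, which would cover PD after SD. That would make the separate row for PD after PR/CR redundant, and it fits poorly with another row that lists SD/NE as previous statuses.

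A reader might also infer that the table covers no growth after a stable scan, or that it leaves most imaging progressions unclassified. The documents support neither. Worse neurology with a stable or increasing steroid dose has a row (Confirmed PD), and the illustrative share runs from 23% to 79% on assumed inputs.

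**Conclusion.** The point holds in limited form, for patients with measurable disease.

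(a) The SD-after-Preliminary-CR row is wrong as written where new sites are Yes. It contradicts 11.2, 11.5 item 2 and footnote a. Each affected patient would be recorded as a confirmed responder, with the PFS date at least one interval (8 ± 4 weeks) late. The documents give no CR rate, so the number of patients is unknown; it is probably small.

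(b) With stable or better neurology, the table lacks rows for PD after SD and for PD with a new measurable site after PR or CR. The first of these is classified and dated by 11.5 and 11.9. The share of progressions falling in these gaps cannot be determined from the documents.

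PFS and response are affected. OS, the primary endpoint, does not use the table. The conclusion assumes that the 12 rows survived text extraction from the PDF, as they appear to have done.

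**What to change.** For endpoint derivation only, before PFS and response are analyzed:

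1. In the SD-after-Preliminary-CR row, change new sites to No. Add a row giving Preliminary PD, dated to that scan, for new measurable disease after Preliminary CR. The four contradictory combinations disappear.
2. In the PD / Not Evaluated row, add SD to the previous-scan cell. Coverage of PD after SD with stable or better neurology goes from 0 of 8 to 8 of 8.
3. In the row for PD after PR/CR, change new sites to Yes or No. Coverage goes from 4 of 8 to 8 of 8.
4. Reconcile the Confirmed PD row's requirement of steroid usage Yes with 11.5. Edits 1 to 3 do not touch it, so the example above, in a patient off steroids, would still have no row at scan 3.
5. State that PFS and response dates follow the measurement-based definitions, and reconcile 11.2, 11.5, 11.8 and 11.9 accordingly.

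These sections also direct when therapy stops. Nothing here says which of them governs that; on stopping, the passages need only be reconciled with one another.

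The cost is three cells, one row, one reconciled condition and one sentence. Statuses can be re-derived from measurements, neurological status and steroid data that the protocol already collects.

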11.9 Detailed Modified Radiographic Response Assessment

The diagram below indicates the modified RANO treatment algorithm for the assessment of modified radiographic response in newly diagnosed glioblastoma:

Preliminary Radiographic Progression

If the lesion size has increased $\geq 25\%$ sum of bidirectional product between MRI Scan 1 and N, these patients should be categorized as “preliminary radiographic progression”. If the investigator believes the patient can safely continue on therapy, then they should continue to treat and acquire a follow-up confirmatory scan [MRI(N + 1)] at the next scan interval (8 weeks \pm 4 weeks from MRI Scan (N) or no less than 4 weeks minimum duration between preliminary PD and confirmed PD scans) to verify tumor growth and progression. For patients with gross-total resection (GTR) and no measurable enhancing disease, *preliminary radiographic progression* is defined as a transition from *no measurable disease* to *non-measurable (but present) disease* ($<10\text{mm} \times 10\text{mm}$) or *measurable disease* ($>10\text{mm} \times 10\text{mm}$). If the investigator feels it is safe to keep the patient on, a confirmatory scan at MRI(N + 1) should be obtained to verify tumor progression.

Confirmed Progression

If the patient has an increase $\geq 25\%$ sum of bidirectional product between MRI Scan N and N + 1, this is “Confirmed Progression”, *the patient should stop therapy* and the date of radiographic progression is the date of suspected progression, MRI(N). If the patient has SD/PR/CR on MRI(N + 1) with respect to MRI(N), PsP is confirmed and the patient should continue on therapy. Patients will then continue on therapy and receive additional follow-up MRI scans [MRI(M)]. If the lesion size has increased $\geq 25\%$ sum of bidirectional product on MRI(M) relative to the smaller of Nadir or MRI(N + 1), then the patient has “Confirmed Progression”, *the patient should stop therapy* and the date of radiographic progression is the new date, MRI(M). For patients with no measurable disease at the Post-RT baseline, “Confirmed Progression” will be defined as a transition from *non-measurable (but present) disease* ($<10\text{mm} \times <10\text{mm}$) on MRI(N) to *measurable disease* ($>10\text{mm} \times 10\text{mm}$) on MRI(N + 1). For patients with confirmed PsP and no measurable disease at Nadir, “Confirmed Progression” should be defined as a transition from *no measurable disease* to *measurable disease* ($>10\text{mm} \times 10\text{mm}$). In all cases, patients with confirmed progression should stop therapy.

Preliminary Radiographic Response

If a measurable lesion has decreased $\geq 50\%$ sum of bidirectional product between MRI(1) and MRI(N), these patients should be categorized as “preliminary radiographic responders” and will be monitored for an additional time point and/or treatment cycle. After an additional cycle of therapy (8 weeks \pm 4 weeks from MRI(N)), patients will receive a confirmatory MRI(N + 1).

Confirmed Radiographic Response

If the lesion(s) have increased $\geq 25\%$ sum of bidirectional product between MRI Scan N and N + 1, (indicating radiographic progression from MRI(N)), this is considered an “unsustained radiographic response” or “pseudoresponse”. These patients should be categorized as “preliminary radiographic progression”. If the investigator believes the patient can safely continue on therapy, then they should continue to treat and acquire a follow-up confirmatory scan [MRI(M)] at the next scan interval (8 weeks \pm 4 weeks from MRI Scan (N+1) or no less than 4 weeks minimum duration between preliminary PD and confirmed PD scans) to verify tumor growth and progression. If the patient has an increase $\geq 25\%$ sum of bidirectional product between MRI Scan N+1 and M, this is “Confirmed Progression”, *the patient should stop therapy* and the date of radiographic progression is the date of suspected progression, MRI(N+1). If the patient has SD/PR/CR on MRI(M) with respect to MRI(N+1), PsP is confirmed and the patient should continue on therapy. Patients will then continue on therapy and receive additional follow-up MRI scans [MRI(M)].

Alternatively, if the lesion has not increased from MRI(N), this is considered a “durable radiographic response,” the patient will continue on therapy, and the date of *preliminary* radiographic progression is the time point of an increase $\geq 25\%$ sum of bidirectional product (from Nadir) during the remainder of the study. The investigator can then decide whether to continue safely on therapy until progression has been confirmed and at the subsequent time point stop therapy if they feel the patient cannot safely continue therapy.

Stable Disease

If the lesion size has not increased or decreased beyond the set thresholds between Scan 1 and N, the patient is considered “stable.” Such patients will continue on therapy, and the date of *preliminary* progression is the time point of an increase $\geq 25\%$ sum of bidirectional product (from Nadir) during the remainder of the study. Upon preliminary progression the investigator can choose to either continue therapy and confirm progression or discontinue therapy. For cases with significant neurologic decline at the time of imaging progression as determined from MRI(N), a confirmatory scan at time point MRI(N + 1) may not be possible or necessary. For these cases, it is appropriate to define MRI(N) as the progression time point.

11.10 Clinical Judgement

Treatment effects, necrosis, vasogenic edema and true tumor progression may appear similar on post contrast brain MRI. There is a continued effort to develop new tools and method to characterize these different outcomes. However, differentiating treatment effects from true progression in patients with high-grade glioma remains an ongoing challenge.

Consequently, we propose to provide some allowance for clinical judgement when deciding whether to discontinue DC vaccination when there is a reasonable doubt regarding disease progression versus treatment effects.

In the event of radiographic changes that meet modified RANO criteria for disease progression in clinically stable or improved patients, vaccination treatment may be continued at the discretion of the PI in consultation with the treating physician, if the PI believes that it is safe to continue therapy and that patients may benefit from the ongoing treatment regimen. Subsequent evaluation by radiographic imaging, clinical evaluation, and/or surgery/biopsy that declares true tumor progression will result in establishing the date of tumor progression at the time when the patient first met modified RANO criteria for documented tumor progression. Therefore, it will not be deemed a protocol deviation for patients to have received subsequent DC vaccines during the interval of assessment for resolving tumor progression. Given the primary endpoint of overall survival for this phase 2 study and above described difficulties in radiographic assessment in this patient population, an allowance for clinical judgement on treatment discontinuation is warranted.

11.11 Confirmation of Tumor Progression by Histopathology

Due to the challenge of recognizing treatment effect from tumor progression, histological confirmation of tumor progression should be obtained when clinically indicated to avoid premature termination of effective treatment or continuing ineffective treatment. Tissue obtained by biopsy or resection will be used to confirm tumor progression histologically. If tumor progression is confirmed, ongoing treatment will be stopped and best of available care at the time of confirmed progression will be discussed with the patient. If obtained in sufficient quantity, available tissue will be used to evaluate cellular infiltration and CMV antigen expression at the tumor site.

In the event that histopathology reveals inflammatory response, indicating toxic or therapeutic responses and not tumor progression, the patient may resume ongoing treatment at the discretion of the PI in consultation with the treating physician after the patient has recovered from the effect of biopsy/surgery.

